## **4.2 Integration with Standard Treatment of H&N Cancer**

- 4.2.1 The patient will undergo standard clinical assessment and preparation for surgical resection of oral lesions.
- 4.2.2 A standard contrast-enhanced CT scan will be added to the standard surgical procedure, with fiducial markers placed on the patient's skin and with the patient in same position as used during surgery.
- 4.2.3 During the surgery, the superficial disease will be delineated using either a pointing tools tracking the outline of the tumour or using navigated endoscopy. The delineated disease will be registered to the initial CT scan using fiducial markers placed on the patient prior to the CT scan.
- 4.2.4 Patients will receive standard treatment for oral H&N cancer with surgery according to the UHN H&N oncology site policies. Treatment will not be modified based on the results of this study.
- 4.2.5 The radiation oncologist(s) will use the intra-operative CT scan to delineate the GTV as per standard clinical practice.
- 4.2.6 The overlap and differences between the mapped superficial disease and the GTV will be measured.
- 4.2.7 The locations of the disease identified by the CT scanning and the superficial lesion mapping will be correlated with the pathology reports. (See Sections 7.2 and 7.6 below for details)

## **4.3 Integration with Other Studies in Patients with H&N Cancer**

- 4.3.1 Patients who participate in this study will be also be eligible to participate in other biomarker or therapeutic studies aimed at better characterizing the biologic behavior of H&N cancer or improving clinical outcome. Patients will be consented separately for these other studies.

## 5 Study Schema

Tasks highlighted in grey are additional steps not part of standard clinical practice.

## **6 Study Enrollment and Withdrawal**

### **6.1 Inclusion Criteria**

Patients will be eligible for inclusion in this study if they meet all of the following criteria:

- 6.1.1 Age  $\geq$  18 years
- 6.1.2 Histologic diagnosis of oral squamous cell carcinoma
- 6.1.3 Primary cancer of the H&N
- 6.1.4 Intention to treat using surgery.
- 6.1.5 Ability to provide written informed consent to participate in the study

### **6.2 Exclusion Criteria**

- 6.2.1 Prior complete or partial radiation therapy to H&N
- 6.2.2 Prior complete or partial surgery of the tumour
- 6.2.3 Concurrent illness or condition that precludes subject from undergoing endoscopy or CT scanning
- 6.2.4 Psychiatric or addictive disorders that preclude informed consent or adherence to protocol

### **6.3 Criteria for Withdrawal**

- 6.3.1 Subject requests withdrawal from study for any reason

## 7 Study Schedule and Procedures

### 7.1 Clinical Evaluation and Informed Consent

- 7.1.1 Eligible patients are required to provide written, informed consent prior to study participation.
- 7.1.2 The start of treatment for H&N cancer will not be delayed by participating in this study. Surgery will proceed as schedule.

### 7.2 Design & Methodology

- 7.2.1 Using the Somatom FLASH CT scanner in the OR, a contrast-enhanced CT scan using standard Radiation Medicine protocols will be performed minus the use of a head fixation mask. The contrast agent will be Visipaque. The patient will be awake and generally positioned as they would be for the surgery/endoscopy procedure. Fiducial markers will be added to the patient's surface to be used for the registration of the endoscopy to the CT imaging.
- 7.2.2 The patient will be transferred to the operating table that is part of the ZEEGO robotic imaging device. In this transfer, the Zeego table is rotated and extended so that it aligns with the table of the CT scanner tables. A thin carbon fiber board under the patient is lifted and the patient moved to the Zeego table. A similar procedure has been used in other protocols in the GTx OR.
- 7.2.3 Patient is prepared for surgery.
- 7.2.4 Prior to tumour excision, surgeon defines the observable superficial extent of the disease one of two methods, determined at the discretion of the surgeon. One option uses a tracked pointing tool to record its position as the surgeon moves the pointer around the outline of the superficial disease. The other option is to use navigated endoscopy to record video of the superficial disease. (See Section 7.5) The endoscopes used here can be either rigid (with optical tracking) or flexible (using EM tracking)
- 7.2.5 The surgical procedure will continue using standard of care. Immediately prior to resection of the visible tumour, the tissue will be marked to identify visible extent of the superficial disease and the added margin. The navigated endoscopy will be repeated so that it includes these markings.
- 7.2.6 After surgical resection, a cone-beam CT scan will be acquired to define the location of the resected tissue. The cone-beam CT scan will be registered to the pre-resection CT scan for comparison of the resected volume and the disease contoured by the radiation oncologists. (See 7.2.9 below).

- 7.2.7 The resected tissue sample will be imaged again using a small field of view MRI scanner (0.5T) located in the OR. The tissue sample will then be sent to pathology for standard assessment. See Section 7.6 below for details of pathology handling.
- 7.2.8 Following the surgical procedure, the pre-operative CT scan will be evaluated by 3 observers. Each will independently perform contouring of the GTV. These observers will be practicing radiation oncologists at Princess Margaret Cancer Centre.
- 7.2.9 The shape and position of the superficial lesion defined by the tool tracking or navigated endoscopy (7.2.4) will be registered to the CT scan.
- 7.2.10 Pathology reporting will be correlated to the CT image set, allowing for measurements of the correspondence between the pathology and the contouring of the disease using the CT scan and the superficial disease.

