We currently have a clinical trial examining the impact on contouring accuracy by including spatially registered endoscopic imaging to the planning CT. Despite limited enrollment, several of the cases have shown large discrepancies between the CT visible GTV and the GTV contoured when endoscopic information is included.

The proposed study will examine the necessity of endoscopic contouring by comparison with pathology in a limited number of patients with oral cancer that are scheduled for surgical resection. Using image-guided surgery tools very similar to those used in the endoscopic contouring, we will compare GTV delineation of H&N cancers with and without the use of endoscopic contouring to pathologic findings. The study will use resources available in the GTx-OR (described below) to perform endoscopic contouring on oral cancer patients during the surgical procedure, immediately prior to resection.

The resected samples will be processed using whole mount pathology methods. Images of the whole mount tissue sections will be registered with the CT images acquired before and during surgery so that the pathology findings can be spatially correlated with the CT and endoscopic imaging. The pathology findings will also aid in defining the superficial extent of the disease and if these findings correlate with the region defined by the endoscopic imaging.

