### **4 Study Design**

#### **4.1 Overview**

- 4.1.1 This is a single centre, single arm feasibility study comparing target delineation of GTV for H&N cancer to pathology using either standard CT-based contouring or spatially registered endoscopy combined with CT-based contouring.
- 4.1.2 Oral cancer surgery will be performed under image-guidance, including a standard contrast-enhanced CT scan immediately prior to the resection procedure. This CT scan will replicate the standard radiation planning CT scan and will be used for delineation of the GTV-std. External fiducial markers will be placed on the patient for registration of the navigation tools to the CT image coordinate system.
- 4.1.3 During surgery, the superficial lesion will be mapped using either a standard pointing tool that will be used by the surgeon to outline the lesion or navigated endoscopy will be performed of the superficial disease visible in the oral cavity. The endoscopic video will be spatially registered to the prior CT scan and used post-procedure for endoscopic contouring as an aid in delineation of the GTV.
- 4.1.4 The tissue will be marked along all planned excisions and resected using standard protocols. The surgical specimen will be mounted and scanned fresh in the OR using the CT scanner and a small animal MRI for correlative pathology. The sample will be prepared for whole mount pathology mapping by embedding the fixed tissue in a gel. The sample will be imaged again using the small animal MRI. It will then be delivered to pathology whole-mount section and identification of disease margins, both superficial and at depth. Details of the pathology workflow are in Section 7.6.
- 4.1.5 Following the procedure, contouring of the GTV will be performed by a radiation oncologist unfamiliar with the surgery and using only the CT image. The mapping

of the superficial lesion (from 4.1.3) will be added to the CT image and the errors between the standard CT-based contouring and the extent of the superficial lesion will be measured. The standard contours and lesion mapping will be compared to pathology for concordance and volume.

[figure not shown]

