## 7.6 Pathology Correlation Procedures

Specifics of tissue handling:

Notification of a case pathologist (Drs. [name] or [name]) and Surgical Pathology Laboratory Grossing room at UHN by [name] of name, MRN and date of surgery of patient scheduled for oral/tongue resection.

2. Sample taken by GTx staff to Pathology on 2nd floor TGH. Accessioning of surgical specimen by technologist upon arrival from OR and verification of the specimen by case pathologist. Inform biobank personnel that the case may not be biobanked.
3. Fresh sample taken by GTx staff to small animal MRI on 7th floor Princess Margaret Discovery Tower (PMDT). T2-weighted (T2) and T1-weighted imaging of fresh sample within 2 hours of surgery.

4. Sample returned by GTx staff to Pathology on 2nd floor TGH. No incisions in the specimen are allowed to preserve the anatomy. Fixation and processing of the surgical specimen with neutral buffered formalin then overnight fixation of the specimen immersed in formalin. This may include injection of formalin into the specimen.
5. Gross description, including inspection orientation and measuring of the specimen and inking (with multiple colors to determine margin status and to aid in orientation) according to standard operating procedure. Recording of data on a requisition sheet.
6. Removal of stitches and/or sutures of specimen by Head and Neck pathologists/pathology fellow.
7. Gel embedding of sample, including MR visible markers to aid in identifying slice location. Once complete, fixed sample taken by GTx staff to small animal MRI on 7th floor PMDT for T2 and T1-weighted imaging.
8. Sample returned by GTx staff to Pathology on 2nd floor TGH. Sectioning at a 3mm interval will be done by a head and neck pathologist/fellow. Gross digital pictures of each section will be taken. Sections will then be sent for paraffin infiltration by UHN pathology.
9. Histologic wholmount processing (further sectioning to 4-6 $\mu$ m thickness, mounting of sections on slides, staining with hematoxylin and eosin (H&E) stain). Each paraffin bock and slide will contain a label that includes the accession number and a number for identification of a section.

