## 7.7 Metrics

- 7.7.1 Analysis will correlate the pathological sampling to the imaging. Specifically, we will compare the number of samples that show superficial disease and how this matches the location of the GTV as determined by CT imaging alone (GTV-std)

and the location of the GTV as determined by the combination of CT imaging and navigated endoscopy (GTV-endo).

- 7.7.2 Analysis will correlate the pathological sampling to the imaging. Specifically, we will measure the overlap of the pathology with the tumour defined using CT imaging alone, and the overlap of the pathology with the mapping of the superficial extent of the disease determined during surgery using either the pointing tool or navigated endoscopy.
- 7.7.3 Concordance of GTV-std and GTV-endo using conformity indices such as DICE, or STAPLE. These metrics estimate the differences between the GTV contours.

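### Where a resection margin is positive, the 7.7.2 overlap with pathology overstates the surface map's coverage and leaves GTV-std outside the specimen unverified; the protocol sets no rule by margin status.

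*Protocol*

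**What the plan says.** - **Surface map.** Protocol 7.2.4: "Prior to tumour excision, surgeon defines the observable superficial extent of the disease one of two methods", either a tracked pointer or navigated endoscopy.
- **Excision line.** 7.2.5: immediately before resection "the tissue will be marked to identify visible extent of the superficial disease and the added margin". Overview 4.1.4: "The tissue will be marked along all planned excisions and resected using standard protocols". The width of the margin is not given.
- **GTV-std.** 7.2.8: "the pre-operative CT scan will be evaluated by 3 observers. Each will independently perform contouring of the GTV". Under 4.1.5 the contouring is done without knowledge of the surgery, so nothing ties these contours to the excision line.
- **Reference standard.** Section 2.2: "The resected samples will be processed using whole mount pathology methods". Section 9.1.1 expects ten whole-mount specimens from ten patients.
- **Metric.** 7.7.2: "we will measure the overlap of the pathology with the tumour defined using CT imaging alone", and likewise the overlap of pathology with the surface map. It states no region for the calculation and no rule by margin status.
- **Relevant data already obtained.** 7.2.6: "The cone-beam CT scan will be registered to the pre-resection CT scan for comparison of the resected volume" and the contoured disease. 7.6 step 5 includes "inking (with multiple colors to determine margin status and to aid in orientation". Section 7.7 uses neither the resected volume nor margin status.

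**The concern.** One of the two methods being compared, the surgeon's view of the surface, also helps decide which tissue gets histology. The other method, the CT contour, has no such link. The two are therefore not verified equally.

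The pathology contour ends at the cut edge. An overlap computed with no stated region thus treats everything past that edge as disease-free. That is a fair presumption when the margin is clear. It is not when disease reaches the edge, because the reference is then truncated. At stake is the claim the study is meant to inform: how much of the true disease each method captures, and whether CT contour lying outside the specimen is an error or simply tissue nobody examined.

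**Working it through.** The protocol has no figure of its own to reproduce here. The number of specimens, ten, is stated without a derivation. The check is to trace which tissue is examined and then see what the overlap measures can and cannot recover.

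**Notation.** T = true disease, P = resected tissue, M = surface map, G = GTV-std. Pathology sees only T∩P.

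**Step 1: coverage by the map.** M lies inside P by design. True coverage is |M∩T|/|T|; apparent coverage is |M∩T|/|T∩P|. If a fraction f of the disease lies past the cut, true = apparent × (1 − f). With a clear margin f is presumed 0 and the two agree. With a positive margin the apparent figure is an upper bound.

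**Step 2: coverage by GTV-std.** True = apparent × (1 − f) + c × f, where c is the share of the unexamined disease that G reaches. If G does not reach it, c = 0 and coverage is overstated exactly as for the map. If G reaches all of it, c = 1 and coverage is understated. The protocol does not give c.

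**Step 3: Dice for GTV-std (assumed volumes).** Pathology 10 cc, GTV-std 14 cc, overlap 9 cc, of which 2 cc of GTV-std lies outside the specimen.

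| Situation | Calculation | Dice |
|---|---|---|
| Unrestricted, as observed | 2×9/(10+14) | 0.75 |
| Clear margin: true value (no disease past the cut) | 2×9/(10+14) | 0.75 |
| Clipped to the specimen | 2×9/(10+12) | 0.82 |
| Positive margin, 2 cc past the cut, all inside GTV-std | 2×11/(12+14) | 0.85 |
| Positive margin, 2 cc past the cut, none inside GTV-std | 2×9/(12+14) | 0.69 |

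With a clear margin, 0.75 is right and clipping flatters GTV-std by deleting real false positives. With a positive margin, the observed 0.75 is compatible with both 0.69 and 0.85.

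**Step 4: disc model (all geometry assumed).** Map radius 12 mm; GTV-std radius 15 mm, shifted 5, 8 or 12 mm; specimen = map plus a 5 or 10 mm margin.

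- Map inside the specimen: 100% at both margins. After a 3 mm map shift it is still about 100%, and 97% with an assumed 2 mm margin.
- GTV-std outside the specimen: 10%, 23% and 40% with the 5 mm margin; 0%, 2% and 16% with the 10 mm margin.
- Clear margin (disease a 14 mm disc inside the specimen; 5 mm margin, 8 mm shift): Dice for GTV-std is 0.65 unrestricted and 0.65 in truth, but 0.74 if clipped.
- Disease past the cut (union of two 14 mm discs, one centred on the map and one on GTV-std; 5 mm margin, 8 mm shift; f = 0.14): map coverage appears as 0.629 and is 0.629 × 0.86 = 0.54. GTV-std coverage appears as 0.743 and is 0.743 × 0.86 + 1 × 0.14 = 0.78, because here it reaches all the missing disease. Had it reached none, it would be 0.743 × 0.86 = 0.64. Dice appears as 0.75 for GTV-std and 0.77 for the map; against full disease it is 0.84 and 0.70.
- With the 10 mm margin and shifts of 5 or 8 mm, no disease lies past the cut and the effect vanishes.

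**Step 5: how often the rule would be needed.** The protocol gives no positive-margin rate. If it were 10% to 20%, one or two of ten specimens would be expected, and the chance of at least one is 1 − 0.9^10 = 0.65 to 1 − 0.8^10 = 0.89. This measures how likely the situation is to arise, not its effect on any result.

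**The case against.** The strongest case against has four parts.

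- **Every surgical-specimen study has this limit, and an analysis plan could handle it.** 7.7.2 says only that overlap will be measured, so a reader cannot conclude that the sponsor would score every bit of GTV-std outside the specimen as wrong. That stands. But the unequal verification comes from the design, and no analysis plan can create pathology for tissue left in the patient. The protocol names the metric, so the qualification can sit beside it.
- **The protocol already compares the resected volume with the contours (7.2.6) and determines margin status (7.6).** True, and this undercuts any claim that it ignores the boundary. Neither supplies histology beyond the cut, and 7.7 does not bring them into the overlap measures.
- **With a clear margin, GTV-std outside the specimen is over-contour.** This stands and limits the point. A reader might infer that all overlaps should be clipped to the specimen, or that the rise from 0.75 to 0.82 measures bias. The clear-margin rows above show otherwise.
- **The direction is not established.** This also stands. A reader might infer a general tilt toward the surface map. Truncated disease can inflate GTV-std's coverage too, and the reversed ranking in the disc model is one chosen geometry. Superficial disease that CT missed but that lies within the map or the added margin is examined.

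It would also be too strong to say the map is always fully verified. Tracking accuracy is about 3 mm, resection follows standard practice, and a surface marking does not define the deep boundary.

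Two passages might seem to fill the gap. The protocol summary mentions biopsy sampling, but sections 4 and 7 describe no biopsy outside the specimen. Section 9.1.1 allows other pathology findings, but conditionally and located through the excision markings.

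**Conclusion.** The point holds for positive-margin specimens. There the map's coverage is an upper bound, as is that of GTV-std where it does not reach past the cut, and GTV-std outside the specimen is unverified. For clear-margin specimens the unrestricted overlap is appropriate, on the presumption that no disease lies past the cut.

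The size and net direction cannot be derived from the protocol: margin width, tumour size, GTV displacement and positive-margin rate are all absent. The figures above are illustrations on assumed inputs. In a descriptive ten-patient feasibility study this is a cheap improvement that changes what may be said about coverage. It does not show that the comparison is invalid.

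**What to change.** In 7.7.2:

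1. Keep the unrestricted overlap as the main figure for clear-margin specimens. Do not clip all cases to the specimen.
2. Report the GTV-std volume outside the resected volume (from the registered cone-beam CT in 7.2.6) separately by margin status: presumed over-contour if clear, unverified if positive.
3. For positive-margin specimens, give overlap within the specimen only as a secondary figure. Label coverage an upper bound for the map, and for GTV-std where it does not extend past the cut; otherwise label GTV-std coverage as covering examined disease only.
4. Show the summary with and without positive-margin specimens.

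Apply the same rule to GTV-endo, and name margin status as a data item in 7.8.

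No added patients or imaging and no change to surgery is involved. The cost is an extra table row, a more qualified statement about coverage, and dependence on how well the cone-beam CT delineates the resected volume, for which the protocol gives no accuracy.

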### **7.3 Intraoperative CT Scanning**

- 7.3.1 The CT scan will be an additional scan of the patient beyond standard of care. The typical dose for a CT scan of the head is 2-3 mSv. This is similar to the annual background radiation exposure in Canada. The contrast agent is Health Canada approved.

### **7.4 Equipment and Software for Endoscopic Contouring**

- 7.4.1 The navigation tools and image guidance software platform used in this protocol have been developed within UHN. The tools include real-time optical and electromagnetic tracking (using commercially available equipment from NDI, Waterloo, ON) of surgical instruments and endoscopes co-registered to CT and MR imaging and display of the imaging information using augmented visualization methods. The necessary functions include:

- reading of CT images and data,
- tracking of EM sensors, calibration of endoscopic images,
- registration of CT image and EM coordinate spaces,
- registration of video images to CT images,
- selection of video frames for contouring,
- contouring on endoscopic images and

- export of endoscopic contours for reading by the treatment planning system.

7.4.2 This package has been demonstrated in several previous and current REB protocols:

UHN REB 11-0660-CE, Localized Intraoperative Virtual Endoscopy (LIVE) for Surgical Guidance in Sinus and Skull Base Patients

UHN REB 12-5315: The Translational Research Image-Guided Operating Room (TRIGORA): Intraoperative 3D Imaging for Head & Neck Surgical Patients

UHN REB 13-5914-C: Comparing Target Delineation of Head and Neck Cancers With and Without the Aid of Spatially Registered Endoscopy

UHN REB 15-9147-CE: Intraoperative 3D Imaging and Navigation for Patients with Benign Bone Tumours

## 7.5 Endoscopy Procedures

7.5.1 The endoscopy procedure will follow the CT scan and patient transport, which will be within 30-40 minutes following the CT scan. If necessary, immobilization devices may be used to fix the patient in the same position for endoscopy as used during the CT scan. Small plastic fiducial markers will be temporarily added to the patient using double sides tape. Once the patient is in place on the surgical table, CT to EM registration will be performed. The fiducial markers placed on the patient will be identified and located in both the CT image and in real space using the EM secondary pointing tool.

